### 6.6.3. Secondary Efficacy Analysis

The following secondary endpoints will be analyzed as dichotomous endpoints and analogously to the primary endpoint:

- proportion of subjects achieving PASI90 at Week 16 in subjects with  $\geq 3\%$  BSA psoriasis at baseline
- proportion of subjects achieving resolution of enthesitis at Week 16 in subjects that had enthesitis (LEI  $> 0$ ) at baseline
- proportion of subjects achieving MDA at Week 16
- proportion of subjects achieving ACR20 at Week 16

- proportion of subjects achieving improvement in PsAID of at least 3 units at Week 16 compared to baseline in subjects with PsAID  $\geq 3$  at baseline

Subjects who have missing data at Week 16 will be imputed as nonresponders and included in the analysis.

The secondary endpoint of change in physical function of HAQ-DI from baseline to Week 16 will be analyzed using the mixed-effects model for repeated measures (MMRM) that includes data at postbaseline visits up to the time point of interest. Subjects that have a baseline value and at least 1 post-baseline value are included in the analysis. The model includes the baseline physical function of HAQ-DI, treatment group, and stratification variables, visit week as fixed effects and subject being the random effect. An unstructured variance-covariance matrix will be used. Other variance-covariance matrices, such as autoregressive, and compound-symmetric will be considered in this order if the model does not converge. The Kenward-Roger method will be used to estimate the degrees of freedom. Missing change scores will not be imputed using the MMRM approach. The least squares (LS) means and 95% CIs of the difference in mean change from Baseline in HAQ-DI between each dose regimen of izokibep group and placebo group from MMRM will be provided. Sample SAS code is given as following:

```
proc mixed;
  class week subjectid treatment(ref = "placebo");
  model change_y = baseline_y treatment week prior_tnfi baseline_lei
  repeated week / subject = subjectid (treatment) TYPE = UN;
  lsmeans treatment * week /slice = week cl;
  slice treatment * week/ sliceby = week pdiff cl;
run;
```

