9.1. Statistical Hypotheses

The primary objective of this study is to demonstrate that izokibep (160 mg dosed QW or 160 mg dosed Q2W) is superior to placebo in the proportion of subjects achieving ACR50 at Week 16 of the study. The statistical null and alternative hypotheses to be used to assess the primary objective are:

$$H_0: \pi_{ABY} - \pi_{PBO} = 0$$

$$H_A: \pi_{ABY} - \pi_{PBO} \neq 0$$

Where π_{ABY} and π_{PBO} are the proportion of subjects achieving ACR50 at Week 16 among subjects randomly assigned to receive izokibep and placebo, respectively. One set of hypotheses will be tested for each dose frequency of izokibep 160 mg (QW and Q2W).

Analogous statistical hypotheses will be used for the secondary objective of assessing the proportion of subjects achieving PASI90 at Week 16 among subjects with $\geq 3\%$ BSA psoriasis at baseline, the proportion of subjects achieving resolution of enthesitis at Week 16 among subjects that had enthesitis at baseline, achievement of MDA at Week 16, the proportion of subjects achieving ACR20 at Week 16 compared to baseline, the proportion of subjects achieving improvement in PsAID of at least 3 units at Week 16 compared to baseline in subjects with PsAID ≥ 3 at baseline.

The statistical null and alternative hypotheses to be used to assess the secondary objective of change in physical function of HAQ-DI from baseline to Week 16 are:

$$H_0: \mu_{ABY} - \mu_{PBO} = 0$$

$$H_A: \mu_{ABY} - \mu_{PBO} \neq 0$$

Where μ_{ABY} and μ_{PBO} are the mean change from baseline to Week 16 among subjects randomly assigned to receive izokibep and placebo, respectively. One set of hypotheses will be tested for each dose frequency of izokibep 160 mg (QW and Q2W).

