## 6.6. Efficacy

Hypotheses tested will be adjusted to control the familywise error rate in the strong sense at  $\alpha = 0.05$ , 2-sided.

The statistical comparisons for the primary efficacy endpoint and the secondary endpoints, all at Week 16, will be carried out in sequential order. The primary endpoint, comparing izokibep dosed QW to placebo, will be tested first, with significance concluded if  $p < 0.05$ .

Testing of secondary endpoints, comparing izokibep dosed QW to placebo, will only be carried out if all prior tests, including the tests of the primary endpoint, first show significance with  $p < 0.05$ . If all primary and secondary endpoints, comparing izokibep doses QW to placebo, are significant, testing of izokibep doses Q2W to placebo will begin and follow the same order. As long as all prior tests are significant, testing will proceed in the following order:

- The first secondary endpoint, achieve PASI90 at Week 16 in subjects with  $\geq 3\%$  BSA psoriasis at baseline, comparing izokibep dosed QW to placebo.
- The second secondary endpoint, achieving resolution of enthesitis at Week 16 in subjects that had enthesitis (LEI  $> 0$ ) at baseline, comparing izokibep dosed QW to placebo.
- The third secondary endpoint, achieving MDA at Week 16, comparing izokibep dosed QW to placebo.
- The fourth secondary endpoint, achieving ACR20 at Week 16, comparing izokibep dosed QW to placebo.
- The fifth secondary endpoint, achieving improvement in PsAID of at least 3 units at Week 16 compared to baseline in subjects with PsAID  $\geq 3$  at baseline, comparing izokibep dosed QW to placebo.
- The sixth secondary endpoint, change in physical function of HAQ-DI from baseline to Week 16, comparing izokibep dosed QW to placebo.
- The primary endpoint, achieving ACR50 at Week 16, comparing izokibep dosed Q2W to placebo.
- The first secondary endpoint, achieve PASI90 at Week 16 in subjects with  $\geq 3\%$  BSA psoriasis at baseline, comparing izokibep dosed Q2W to placebo.
- The second secondary endpoint, achieving resolution of enthesitis at Week 16 in subjects that had enthesitis (LEI  $> 0$ ) at baseline, comparing izokibep dosed Q2W to placebo.
- The third secondary endpoint, achieving MDA at Week 16, comparing izokibep dosed Q2W to placebo.
- The fourth secondary endpoint, achieving ACR20 at Week 16, comparing izokibep dosed Q2W to placebo.

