#### 6.6.4. Supplementary Analyses for the Secondary Efficacy Analysis

Sensitivity analyses will use analysis of covariance on change in physical function of HAQ-DI from baseline to Week 16, with stratification variables used for randomization also included as covariates, along with baseline physical function of HAQ-DI.

Sensitivity analysis for physical function of HAQ-DI will also use multiple imputations. Physical function of HAQ-DI missing as Week 16 will be replaced with the imputed value from the imputation dataset. The imputation dataset will be created from the placebo subjects who have complete data.

**Multiple Imputation:** Multiple imputations will be implemented to replace missing endpoint data using multiple draws from a posterior predictive distribution estimated from the placebo group only. For HAQ-DI at Week 2, 4, 12, and 16, assuming monotone missingness

pattern, missing HAQ-DI will be imputed using previous HAQ-DI (except for Week 2) up to the time point of interest and randomization strata using placebo group only. Missing HAQ-DI in the placebo group and two izokibep groups will be imputed. Monotonicity in missing data will first be imputed with MCMC. The resulting data will then be processed sequentially by repeatedly calling SAS® PROC MI to impute missing outcomes. A total of 100 imputations will be imputed to form the complete data set with a pre-specified seed (36767) to ensure reproducibility. These multiple imputed data sets will then be analyzed by using the same method for the HAQ-DI endpoint analysis as specified in Section 6.6.3. The final inference on treatment difference is conducted from the multiple datasets using Rubin's combining rules. Other imputation, fully conditional specification method may be implemented if the multiple imputation model does not converge.

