- ACR70 at Weeks 16, 24, and 52
- DAPSA  $\leq 14$  at Weeks 16, 24, and 52
- cDAPSA  $\leq 14$  at Weeks 16, 24, and 52
- DAPSA  $\leq 4$  at Weeks 16, 24, and 52
- cDAPSA  $\leq 4$  at Weeks 16, 24, and 52
- PASI75 at Weeks 16, 24, and 52
- PASI100 at Weeks 16, 24, and 52
- MDA at Weeks 24, and 52
- VLDA at Weeks 16, 24, and 52
- Resolution of dactylitis at Weeks 16, 24, and 52 among those with dactylitis at baseline
- ACR50 at Weeks 24 and 52
- PASI90 at Weeks 24 and 52 among those with  $\geq 3\%$  BSA psoriasis at baseline
- Resolution of enthesitis (LEI = 0) at Weeks 24 and 52 among those with LEI  $> 0$  at baseline
- Resolution of enthesitis (SPARCC = 0) at Weeks 24 and 52 among those with SPARCC  $> 0$  at baseline
- PsAID response at Weeks 24 and 52
- ACR20 at Weeks 24 and 52
- Occurrence of enthesitis (LEI  $> 0$ ) at weeks 4, 8, 12 and 16, among subjects with no enthesitis (LEI = 0) at baseline
- Decrease of at least 2 in LEI, among subjects with baseline LEI of at least 2, at weeks 4, 8, 12 and 16.

The following continuous endpoints will be analyzed at week 16 with an MMRM model as specified in sec 6.6.3, and after week 16 with standard summary statistics for continuous endpoints. LS mean changes and associated SEs with associated 95% CI and p-values will be presented. Models through week 16 will include all data up to Week 16. The following continuous endpoints after Week 16 will be analyzed according to the four randomized treatment groups. Mean changes and associated SEs along with 95% CI according to the four randomized treatment groups will be presented without strata. No p-values will be reported.

- Change from baseline in DAS28-CRP at Weeks 16, 24, and 52
- Change from baseline in DAPSA/cDAPSA at Weeks 16, 24, and 52
- Change from baseline in PASDAS at Weeks 16, 24, and 52

- Change from baseline in mNAPSI at Weeks 16, 24, and 52 in those with nail psoriasis at baseline
- Change from baseline in mTSS at Weeks 16 and 52
- Change from baseline in SPARCC enthesitis score at Weeks 16, 24, and 52 in those with enthesitis at baseline (SPARCC>0)
- Change from baseline in spinal pain NRS at Weeks 16, 24, and 52
- Change from baseline in spine pain NRS in those with sacroiliitis on pelvic x-ray
- Change from baseline in spine pain NRS in those with investigator assessed spinal involvement
- Correlation of investigator assessed spinal involvement with sacroiliitis on x-ray

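### The HAQ-DI repeated-measures model has no treatment-by-visit term, so as written it does not estimate the Week 16 difference that the alpha-controlled test is about

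*SAP*

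**What the plan says.** Protocol 9.1 sets the HAQ-DI hypothesis at a single visit: the two parameters "are the mean change from baseline to Week 16 among subjects randomly assigned to receive izokibep and placebo". SAP 6.6 puts the comparison into the alpha-controlled sequence: "The sixth secondary endpoint, change in physical function of HAQ-DI from baseline to Week 16, comparing izokibep dosed QW to placebo". It is step 7 of 14, and steps 8 to 14 are the Q2W tests.

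SAP 6.6.3 uses all post-baseline visits up to the time point of interest, with an unstructured covariance matrix. Its fixed effects are given in one sentence: "The model includes the baseline physical function of HAQ-DI, treatment group, and stratification variables, visit week as fixed effects and subject being the random effect". The sample code has the same main effects: "model change_y = baseline_y treatment week prior_tnfi baseline_lei". It then requests output by week, for example "slice treatment * week/ sliceby = week pdiff cl". The sentence on LS means and confidence intervals does not tie the reported difference to Week 16.

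Protocol 9.3.3 describes the model with baseline, treatment and strata only, without a visit term. No other section of either document adds an interaction.

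SAP 6.6.4 plans a single-visit analysis as a sensitivity analysis: "Sensitivity analyses will use analysis of covariance on change in physical function of HAQ-DI from baseline to Week 16". Its multiple-imputation analysis is "analyzed by using the same method for the HAQ-DI endpoint analysis as specified in Section 6.6.3". SAP 6.6.5 sends the continuous exploratory endpoints through the same model: "Models through week 16 will include all data up to Week 16".

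**The concern.** A repeated-measures model with treatment and visit as main effects assumes that the treatment difference is the same at every visit. Its treatment estimate pools Weeks 2, 4, 12 and 16. If the effect builds up over time, the pooled value understates the Week 16 effect, and its confidence interval is centred in the wrong place. If the effect fades, the model can reject when there is no Week 16 difference. In either case the quantity tested is not the one in the hypothesis.

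The output lines point to a different model from the one specified. Two programmers could therefore produce different estimates and p-values for a confirmatory test, and this test decides whether any Q2W comparison is made.

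**Working it through.** **Inputs from the documents.** HAQ-DI visits through Week 16 are Weeks 2, 4, 12 and 16 (SAP 6.6.4). There are 100 subjects per 160 mg arm and 100 on placebo (SAP 2.1). The level is two-sided 0.05 (SAP 6.6). Neither document gives a HAQ-DI effect, SD, correlation, time course or power, so there is no stated figure to reproduce.

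**Assumed inputs.** Week 16 effect 0.25 (benefit shown as positive), SD 0.55 at every visit, complete data. Three correlation structures: compound symmetry (CS) 0.6, and autoregressive 0.93 or 0.97 per week.

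**Formulas.** Let S be the covariance matrix of the four visits, 1 a vector of ones and d the vector of true visit differences.
- Weights of the main-effects estimate: w = S⁻¹1 / (1′S⁻¹1). Its expected value is w′d.
- SE of the main-effects estimate: √[(2/100) / (1′S⁻¹1)].
- SE of the Week 16 contrast: 0.55 × √(2/100) = 0.078.
- Power of the Week 16 contrast: 0.25/0.0778 = 3.21, and Φ(3.21 − 1.96) = 0.90.

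**Weights and SE of the main-effects estimate.**

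| Correlation | Weights, Weeks 2/4/12/16 | SE |
|---|---|---|
| CS 0.6 | 0.25/0.25/0.25/0.25 | 0.065 |
| 0.93 per week | 0.36/0.12/0.14/0.38 | 0.064 |
| 0.97 per week | 0.43/0.06/0.08/0.44 | 0.071 |

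**Worked case: CS, effect at 40/60/90/100% of its Week 16 size.**
- Share recovered: 0.25 × (0.40 + 0.60 + 0.90 + 1.00) = 0.725, so the estimate is 0.725 × 0.25 = 0.181.
- Power: 0.1813/0.0651 = 2.785, and Φ(2.785 − 1.96) = 0.795.
- Coverage of 0.25: the bias is (0.25 − 0.1813)/0.0651 = 1.056 SE, and Φ(1.96 − 1.056) − Φ(−1.96 − 1.056) = 0.816.

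**Range over the three correlation structures.** The Week 16 contrast has power 90% and coverage 95% in every case below.

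| Effect at Weeks 2/4/12/16, % of Week 16 | Share recovered | Power | Coverage of Week 16 effect |
|---|---|---|---|
| (a) 40/60/90/100 | 71–73% | 71–81% | 81–83% |
| (b) 25/50/85/100 | 64–65% | 62–73% | 72–75% |
| (c) 60/80/100/100 | 82–85% | 82–91% | 90–91% |
| (d) constant | 100% | 94–98% | 95% |

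**SD growing over visits** (assumed ratios 0.70/0.80/0.95/1.00). Profile (a) then recovers 48% (CS), 53% (0.93) or 35% (0.97). The 35% is a corner case: its weights are 1.46/−0.56/−0.04/0.15. The CS case, with weights 0.648/0.323/0.045/−0.015, is less extreme, but there too the estimate rests almost wholly on Weeks 2 and 4.

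**Second set of assumptions, by simulation** (4,000 runs, SD 0.50, CS 0.6, covariance estimated).

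| True effect at Weeks 2/4/12/16 | Main-effects model rejects | Week 16 contrast rejects |
|---|---|---|
| 0.08/0.14/0.24/0.28 | 0.874 (mean estimate 0.186) | 0.973 (mean estimate 0.280) |
| 0.20/0.20/0.10/0 | 0.569 | 0.052 |
| none at any visit | 0.056 | 0.058 |

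For the early-only effect in the second row, the main-effects rejection rate by formula runs from 0.50 to 0.99 over four covariance structures: SD equal at 0.50 or rising from 0.35 to 0.55, each with CS 0.6 or first-order autoregression 0.7 between successive visits.

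**The case against.** The strongest reply is that the plan names its target and its contrast, and only a model term is missing. The endpoint is placed at Week 16 throughout, the only contrasts in the code are by week, and nothing requests an overall treatment LS mean. The sample is visibly rough. The MODEL line lacks its closing semicolon, so its end may be lost, and the Kenward-Roger method required by the prose does not appear. The protocol's covariate list omits even the visit term, which suggests shorthand and not a deliberate choice of a constant effect.

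Much of this is fair. An interaction was probably intended, and the MODEL line is weak evidence by itself. But the prose in SAP 6.6.3 is a complete sentence that lists the fixed effects, and it omits the term too. The estimator of a confirmatory test should not have to be inferred from output lines that conflict with the stated model.

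It is also true that the size rests wholly on assumptions, that power can go either way, and that the primary endpoint is untouched. The Week 16 ANCOVA targets the right quantity, but as a sensitivity analysis it cannot stand in for step 7 of the sequence.

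**Conclusion.** The concern holds. As written, the model gives a weighted average difference over Weeks 2 to 16, not the Week 16 difference in the hypothesis. Read through its output lines, the section asks for a contrast that its model does not contain.

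The consistent fault is bias for Week 16 whenever the effect changes over time. Under the equal-variance assumptions, 64–85% of the Week 16 effect is recovered for the three rising profiles, with coverage of 72–91%. Power may be lower, similar or higher than the 90% of a Week 16 contrast. The test keeps its level when there is no effect at any visit. It does not keep it for a Week 16 null with an earlier effect, so the claimed strong familywise control is not assured under the literal model.

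The multiple-imputation analysis inherits the problem. So do exploratory endpoints with several visits by Week 16, such as DAS28-CRP and DAPSA. With only Weeks 12 and 16 (SF-36, PASDAS) and equal variances, the weights are 0.5/0.5 and recovery is 95% for (a) and 92.5% for (b), a small loss. These are examples, not a full list. Endpoints first measured after baseline at Week 16 (FACIT-F, spinal pain, mTSS) are unaffected. The point should be fixed, but it does not threaten the primary result.

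**What to change.** In SAP 6.6.3, add treatment-by-visit to the fixed effects in the prose and `treatment*week` to the sample MODEL statement. State that the confirmatory HAQ-DI test for each regimen is the Week 16 treatment difference from that term. Sections 6.6.4 and 6.6.5 then follow by reference. At the same time, the description of subject as a random effect can be aligned with the REPEATED statement and unstructured covariance, and the Kenward-Roger option added to the code.

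The cost is one sentence and one term, and a few degrees of freedom. If the effect is constant across visits, power falls from 94–98% to about 90% under the assumptions above. No new data are needed. Protocol Section 9 describes itself as a summary, so an SAP clarification before unblinding is enough and no protocol amendment is required.

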#### 6.6.4. Supplementary Analyses for the Secondary Efficacy Analysis

Sensitivity analyses will use analysis of covariance on change in physical function of HAQ-DI from baseline to Week 16, with stratification variables used for randomization also included as covariates, along with baseline physical function of HAQ-DI.

Sensitivity analysis for physical function of HAQ-DI will also use multiple imputations. Physical function of HAQ-DI missing as Week 16 will be replaced with the imputed value from the imputation dataset. The imputation dataset will be created from the placebo subjects who have complete data.

**Multiple Imputation:** Multiple imputations will be implemented to replace missing endpoint data using multiple draws from a posterior predictive distribution estimated from the placebo group only. For HAQ-DI at Week 2, 4, 12, and 16, assuming monotone missingness

pattern, missing HAQ-DI will be imputed using previous HAQ-DI (except for Week 2) up to the time point of interest and randomization strata using placebo group only. Missing HAQ-DI in the placebo group and two izokibep groups will be imputed. Monotonicity in missing data will first be imputed with MCMC. The resulting data will then be processed sequentially by repeatedly calling SAS® PROC MI to impute missing outcomes. A total of 100 imputations will be imputed to form the complete data set with a pre-specified seed (36767) to ensure reproducibility. These multiple imputed data sets will then be analyzed by using the same method for the HAQ-DI endpoint analysis as specified in Section 6.6.3. The final inference on treatment difference is conducted from the multiple datasets using Rubin's combining rules. Other imputation, fully conditional specification method may be implemented if the multiple imputation model does not converge.

### **6.6.5. Exploratory Analysis**

Exploratory endpoints will be analyzed analogously to primary and secondary endpoints, with the exception of a prespecified alpha-controlling testing strategy. Exploratory endpoints of dichotomous measurements will be analyzed analogously to primary endpoints. Exploratory endpoints of continuous measurements will be analyzed analogously to the secondary endpoint of change in physical function of HAQ-DI from baseline to Week 16. P-values for exploratory endpoints will be considered descriptive and not considered conclusive. A summary table of all primary, secondary and exploratory endpoints will be presented using point estimates only, to visually assess izokibep 160 mg dosed QW, izokibep 160 mg dosed Q2W, izokibep 80 mg dosed Q4W and placebo.

All primary, secondary and exploratory endpoints defined for comparing izokibep 160 mg QW or izokibep 160 mg Q2W to placebo will also be reported for comparing izokibep 80 mg Q4W to placebo.

Dose-response will be investigated through analyses of the primary and secondary endpoints, which will use all four treatment arms (izokibep 160 mg QW, izokibep 160 mg Q2W, izokibep 80 mg Q4W and placebo) in a single analysis for each endpoint. A p-value for the global test of the hypothesis that all groups have identical response rates will be reported for each endpoint, not subject to type I error rate control or any multiple comparison procedure. P-values will also be reported for all pairwise comparisons for each endpoint. Dose-response relationships will be assessed qualitatively from these analyses. Due to the error in dose sequence in the Q2W and Q4W arms, additional investigations will include assessment of endpoints that may be achieved earlier, including ACR20 and PASI75 at week 4 (at which time all subjects received correct dose sequencing).

The following binary endpoints before or on Week 16 will be analyzed analogously to the primary endpoints of ACR50 at Week 16. The number and proportion of subjects for binary

endpoints in each treatment group will be reported without strata along with Clopper-Pearson 95% CI. Common risk difference with Cochran-Mantel-Haenszel weighting will be used to calculate a 95% CI, and p-values from the stratified test will be reported as well. The binary endpoints after week 16 will include number and proportion along with Clopper-Pearson 95% CI without strata according to the four randomized treatment groups. No p-value will be reported.

- ACR70 at Weeks 16, 24, and 52
- DAPSA  $\leq 14$  at Weeks 16, 24, and 52
- cDAPSA  $\leq 14$  at Weeks 16, 24, and 52
- DAPSA  $\leq 4$  at Weeks 16, 24, and 52
- cDAPSA  $\leq 4$  at Weeks 16, 24, and 52
- PASI75 at Weeks 16, 24, and 52
- PASI100 at Weeks 16, 24, and 52
- MDA at Weeks 24, and 52
- VLDA at Weeks 16, 24, and 52
- Resolution of dactylitis at Weeks 16, 24, and 52 among those with dactylitis at baseline
- ACR50 at Weeks 24 and 52
- PASI90 at Weeks 24 and 52 among those with  $\geq 3\%$  BSA psoriasis at baseline
- Resolution of enthesitis (LEI = 0) at Weeks 24 and 52 among those with LEI  $> 0$  at baseline
- Resolution of enthesitis (SPARCC = 0) at Weeks 24 and 52 among those with SPARCC  $> 0$  at baseline
- PsAID response at Weeks 24 and 52
- ACR20 at Weeks 24 and 52
- Occurrence of enthesitis (LEI  $> 0$ ) at weeks 4, 8, 12 and 16, among subjects with no enthesitis (LEI = 0) at baseline
- Decrease of at least 2 in LEI, among subjects with baseline LEI of at least 2, at weeks 4, 8, 12 and 16.

The following continuous endpoints will be analyzed at week 16 with an MMRM model as specified in sec 6.6.3, and after week 16 with standard summary statistics for continuous endpoints. LS mean changes and associated SEs with associated 95% CI and p-values will be presented. Models through week 16 will include all data up to Week 16. The following continuous endpoints after Week 16 will be analyzed according to the four randomized treatment groups. Mean changes and associated SEs along with 95% CI according to the four randomized treatment groups will be presented without strata. No p-values will be reported.

- Change from baseline in DAS28-CRP at Weeks 16, 24, and 52
- Change from baseline in DAPSA/cDAPSA at Weeks 16, 24, and 52
- Change from baseline in PASDAS at Weeks 16, 24, and 52

- Change from baseline in mNAPSI at Weeks 16, 24, and 52 in those with nail psoriasis at baseline
- Change from baseline in mTSS at Weeks 16 and 52
- Change from baseline in SPARCC enthesitis score at Weeks 16, 24, and 52 in those with enthesitis at baseline (SPARCC>0)
- Change from baseline in spinal pain NRS at Weeks 16, 24, and 52
- Change from baseline in spine pain NRS in those with sacroiliitis on pelvic x-ray
- Change from baseline in spine pain NRS in those with investigator assessed spinal involvement
- Correlation of investigator assessed spinal involvement with sacroiliitis on x-ray
- Change from baseline in SF-36 total score, PCS, and MCS at Weeks 16, 24, and 52
- Change from baseline in FACIT-F at Weeks 16, 24, and 52
- Change from baseline in LEI enthesitis score at Weeks 16, 24, and 52 in those with enthesitis at baseline (LEI>0)
- HAQ-DI change from baseline to Weeks 24 and 52
- HADS change from baseline to Week 24 and 52

Change from baseline for the individual components of the ACR and MDA scores will be summarized at Week 16. Summary statistics (n, mean, standard deviation, median, minimum, and maximum) will be provided

- Swollen Joint Count
- Tender Joint Count
- SAPVAS
- SGADA
- IGADA
- HAQ-DI
- CRP
- PASI
- BSA
- Tender enthesal points  $\leq$  1 site out of 6 sites included in LEI

The following will be analyzed with a time to event model, using a log rank test with stratification by the factors used to stratify randomization. Subjects who do not achieve the endpoint at or before the week 16 visit will be censored at the time of the last assessment could be derived at or before week 16.

- Time to resolution of enthesitis (LEI = 0) among subjects with enthesitis (LEI = 0) at baseline.
- Time to first achievement of ACR50

- Time to first achievement of PASI90 among subjects with  $\geq 3\%$  BSA psoriasis at baseline
- Time to first achievement of MDA
- Time to first achievement of ACR20
- Time to first achievement of PsAID improvement of at least 3 among subjects with PsAID  $\geq 3$  at baseline
- Time to first achievement of PASI100 among subjects with PsAID  $\geq 3$  at baseline

WPI will be calculated at baseline. WPI is a scale of 0-19, and is a count of how many of 19 body sites the subject reports pain or tenderness in the prior 7 days. Standard summary statistics for binary data will be calculated by baseline WPI (WPI  $\geq 7$  vs.  $< 7$ ) for the following endpoints:

- ACR50 at week 16 (observed responder, observed non-responder, missing)
- LEI responders at week 16 (observed responder, observed non-responder, missing)
- PsAID at week 16 (observed responder, observed non-responder, missing)
- HAQ-DI at week 16: improvement of at least 0.35 (observed responder, observed non-responder, missing)

Area under the curve (AUC) for ACR-N will be calculated for each subject by triangulating the observed values at baseline (by definition ACR-N = 0 at baseline) and weeks 2, 4, 12 and 16. The area for consecutive visits, using nominal time from Week t and Week u, will be calculated as

$$\text{AUC}_{\text{Week } t \text{ to Week } u} = ((u - t) \times (\text{ACR-N}_{\text{Week } t} + \text{ACR-N}_{\text{Week } u})/2$$

The AUC for the period through week 16 will be the sum of the individual values from week 0 through week 16. Any visits at which ACR-N cannot be calculated (including Week 0) will be imputed as ACR-N = 0. In case one or more components of ACR is missing, the smallest value N for which ACR-N is known to be achieved will be used.

Listings of all efficacy data, including derived composite values will be provided for the Full Analysis Set.

PK concentrations will be summarized by dose group and scheduled visit. Summary statistics reported will be number of samples, number of samples that are BLQ, arithmetic mean, standard deviation, coefficient of variation in percent (CV), minimum, median, maximum, geometric mean and the CV of the geometric mean in percent.

